11.1 Change to protocol specified analyses

LLT will only be listed in this study. In the protocol, it was originally planned to analyze LLT as part of the secondary [REDACTED] endpoints. However the device used to measure LLT was unable to provide a credible LLT value if the LLT value was greater than 100 nm.

Therefore as this impacted at least 25% of the LLT values, it was agreed by the clinical trial team with input from upper management to only list the LLT data.

At the time of the second amended Statistical Analysis Plan, subject follow-up is complete and all subjects have exited the study. The study database is not yet locked and masked treatment code has not been broken. Due to the fact that subject follow-up is complete and the current change to analysis strategy is an operational matter with no impact on study design or subject safety, the decision was taken only to amend the Statistical Analysis Plan and not undertake a corresponding amendment to the protocol.

12 Appendix

12.1 SAS code

12.1.1 Mixed model repeated measures

This SAS code will be used for the MMRM analysis for the primary and relevant secondary endpoints.

```
proc mixed data=<analysis dataset>;  
class usubjid treatment visit;  
model <endpoint of interest>=<baseline of endpoint of interest> treatment  
visit treatment*visit/solution ddfm=kr;  
repeated visit / subject=usubjid type=un;  
lsmeans treatment*visit / pdiff=all cl alpha=0.05 slice=visit;  
run;
```

12.2 Imputation rules

12.2.1 AE date imputation

12.2.1.1 AE end date

For the purpose of date imputation, the study treatment follow-up period date is defined as the last available visit date, i.e. including unscheduled visits after the end of study visit.

1. If the AE end date month is missing, the imputed end date should be set to the earliest of the (study treatment follow-up period date, 31DECYYYY, date of death).
2. If the AE end date day is missing, the imputed end date should be set to the earliest of the (study treatment follow up-period date, last day of the month, date of death).
3. If AE year is missing or AE is ongoing, the end date will not be imputed.

If the imputed AE end date is less than the existing AE start date then use AE start date as AE end date.

12.2.1.2 AE start date

AEs with completely missing onset dates will be considered to be treatment emergent. AEs with partially missing onset dates will also be included as treatment emergent when the month (if it exists) and the year occur on or later than the month and year of first administration of study treatment.

Partial AE start dates are imputed with reference to the first administration of study treatment (TRTSTD) as outlined in the table below.

The date value is split into day, month and year sections and referenced in the imputation table as outlined below:

	Day	Month	Year
Partial AE Start Date	Not used	MON	YYYY
Study Treatment Start Date (TRTSTD)	Not used	TRTM	TRTY

The following matrix explains the logic behind the imputation.

Comparison of month section	MON missing	MON<TRTM	MON=TRTM	MON>TRTM
YYYY missing	NC	NC	NC	NC
YYYY<TRTM	(D) = 01JULYYYY Before Study Treatment Start	(C) = 15MONYYYY Before Study Treatment Start	(C) = 15MONYYYY Before Study Treatment Start	(C) = 15MONYYYY Before Study Treatment Start
YYYY=TRTY	(B) = TRTSTD+1 Uncertain	(C) = 15MONYYYY Before Study Treatment Start	(A) = TRTSTD+1 Uncertain	(A) = 01MONYYYY After Study Treatment Start
YYYY>TRTY	(E) = 01JANYYYY After Study Treatment Start	(A) = 01MONYYYY After Study Treatment Start	(A) = 01MONYYYY After Study Treatment Start	(A) = 01MONYYYY After Study Treatment Start

The following table is the legend to the logic matrix.

Relationship	
Before Study Treatment start	Partial date indicates AE start date prior to Study Treatment Start Date
After Study Treatment start	Partial date indicates AE start date after Study Treatment Start Date
Uncertain	Partial date insufficient to determine relationship of AE start date to Study Treatment Start Date
Imputation calculation	
NC / Blank Uncertain	No convention
(A) After Treatment Start or Uncertain	MAX(01MONYYYY, TRTSTD+1)
(B) Uncertain	TRTSTD+1
(C) Before Study Treatment Start	15MONYYYY
(D) Before Study Treatment Start	01JULYYYY
(E) After Study Treatment Start	01JANYYYY

Before imputing the AE start date, find the AE start reference date.

- If the AE end date is complete and the (imputed) AE end date < TRTSTD then AE start reference date = min (informed consent date, earliest visit date).
- Else AE start reference date = TRTSTD

To impute AE start date:

1. If the AE start date year value is missing, the date uncertainty is too high to impute a rational date. Therefore, if the AE year value is missing, the imputed AE start date is set to NULL.
2. If the AE start date year value is less than the study treatment start date year value, the AE started before study treatment. Therefore:
 - a. If AE month is missing, the imputed AE start date is set to the mid-year point (01JULYYYY).
 - b. Else if AE month is not missing, the imputed AE start date is set to the mid-month point (15MONYYYY).
3. If the AE start date year value is greater than the study treatment start date year value, the AE started after study treatment. Therefore:
 - a. If the AE month is missing, the imputed AE start date is set to the year start point (01JANYYYY).
 - b. Else if the AE month is not missing, the imputed AE start date is set to the later of (month start point [01MONYYYY], AE start reference date + 1 day).
4. If the AE start date year value is equal to the study treatment start date year value:
 - a. And the AE month is missing, the imputed AE start date is set to the AE reference start date + 1 day.
 - b. Else if the AE month is less than the study treatment start month, the imputed AE start date is set to the mid-month point (15MONYYYY).
 - c. Else if the AE month is equal to the study treatment start date month or greater than the study treatment start date month, the imputed AE start date is set to the later of (month start point [01MONYYYY], AE start reference date + 1 day).

If complete (imputed) AE end date is available and the imputed AE start date is greater than the (imputed) AE end date, then imputed AE start date should be set to the (imputed) AE end date.

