6.3 Statistical Methods for Safety Analyses

Except otherwise stated, the analysis set for all safety analyses is the Safety Analysis Set as defined in Section 3. Baseline is defined in Section 2.3.

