6.3.2 Adverse Events

The applicable definition of an AE is in the study protocol. All AEs occurring from when a subject signs the ICF to when a subject exits the study will be accounted for in the reporting. Analysis and presentation of AEs occurring during the 2 week saline run-in period (the screening period) will be separated from those occurring during the investigational period where a comparative evaluation (descriptive only) of treatment-emergent AEs (TEAEs) is intended. A TEAE is an event not present prior to exposure to investigational product (SYSTANE BALANCE, REFRESH OPTIVE Advanced/ OPTIVE PLUS [UK]) or any pre-existing event that worsens following exposure to investigational product. The period for TEAE analysis starts from exposure to the investigational product to 1 day following cessation of investigational product (it is not expected for the side effects of the investigational product to last more than 24 hours).

Descriptive summaries (subject counts and percentages, event counts) by study treatment for specific AEs will be presented by primary SOC and PT. The SOCs will be presented in

alphabetical order. PTs will be ordered for each study treatment in decreasing proportion in the SYSTANE BALANCE treatment group of interest (study treatment group 1). In addition to an overall presentation of all AEs, reports will be generated for special classes of AEs such as most frequent AEs, ocular AEs, non-ocular AEs, treatment-related AEs, serious AEs (SAEs), AEs by maximum severity (mild, moderate, severe), and AEs resulting in study treatment discontinuation. The overall presentation of all AEs will also be presented by demographic subgroups of interest (refer to Section 5.3.2 for details).

Both subject and event counts will be presented for AEs. Subject counts refer to the number of subjects with the respective AE of interest. Subjects who experience multiple AEs for a PT will be counted once, similarly for subjects with multiple AEs per SOC, for subject counts. Event counts refer to the number of occurrences of the respective AE of interest, regardless of whether a subject already had this event. However for ocular AEs, if an AE was classified as occurring in both eyes, dependent on the event and at the discretion of the medical team the event may only be counted once.

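### SAP 12.2.1.2 flags adverse events with a missing or partial onset date as treatment-emergent even when their recorded end date is before first dose

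*SAP*

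**What the plan says.** SAP 12.2.1.2 opens with two flagging rules for AEs whose onset date is incomplete:

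- Onset fully missing: "AEs with completely missing onset dates will be considered to be treatment emergent".
- Onset partly missing: "AEs with partially missing onset dates will also be included as treatment emergent when the month (if it exists) and the year occur on" or after those of first dose.

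Neither rule mentions the end date. The start-date imputation further down the same section does use it:

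- Guard: "If the AE end date is complete and the (imputed) AE end date < TRTSTD then AE start reference date" becomes the earlier of the consent date and the earliest visit date. Otherwise the reference date is the first-dose date, TRTSTD.
- Cap: if the imputed start would fall after the end date, the "imputed AE start date should be set to the (imputed) AE end date".
- Exception: "if the AE year value is missing, the imputed AE start date is set to NULL".

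SAP 6.3.2 gives the definition that the flag is meant to implement: "A TEAE is an event not present prior to exposure to investigational product", or a pre-existing event that worsens after exposure. It starts the treatment-emergent period at exposure to the masked product and says that AEs in the saline run-in will be presented separately.

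**The concern.** An AE that was over before the first masked dose meets neither part of the definition in 6.3.2. It was present only before exposure, and it cannot have worsened afterwards. Yet the opening rules of 12.2.1.2 flag it whenever its onset date is incomplete and passes a calendar test.

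That test separates the two periods poorly. The run-in is the 7 to 14 days immediately before first dose, so a run-in AE usually falls in the same month as first dose and nearly always in the same year.

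An event that occurred and resolved on open-label saline can thus be tabulated under a masked product. The section also gives two answers for one event, since the flag says treatment-emergent while the imputed start date says pre-treatment. The SAP does not say which prevails, so two programmers could produce different tables. The treatment-emergent tables also feed the registry postings described in 6.3.2.

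**Working it through.** The plan states no figure on this point, so there is none to reproduce. The check applies the opening rules and the imputation steps to the same events.

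**One event traced through the section.** Screening and consent 8 March, first dose 20 March, onset recorded as March with the day missing, end date 14 March.

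| Rule in 12.2.1.2 | Result |
|---|---|
| Opening rule | March is the month of first dose: treatment-emergent |
| Imputation steps | Reference date 8 March; start = later of 1 March and 9 March = 9 March: pre-treatment |
| Imputation matrix plus cap | TRTSTD + 1 = 21 March, capped at the end date 14 March: pre-treatment |

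If the onset is fully missing, the opening rule again says treatment-emergent, and the imputed start is null. The guard and cap then have nothing to act on.

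**How often the calendar test is passed.** Inputs and assumptions:

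- Run-in length R = 7 or 14 days (protocol synopsis).
- First dose equally likely on each of the 365 dates of one calendar year (2017 was used).
- Onset k days before first dose, k = 1 to R. The end date is complete and lies between the onset and the day before first dose, which leaves k possible end dates.
- All onset/end pairs equally likely. There are R(R + 1)/2 = 28 or 105 pairs per first-dose date, so 365 × 28 = 10,220 or 365 × 105 = 38,325 in all.

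Onset falls in an earlier month than first dose when first dose is on day 1 to k of a month, which is 12k of the 365 dates. Onset k carries weight k, so:

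Share in the same month = 1 − (12/365) × Σk²/Σk

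- R = 7: Σk²/Σk = 140/28 = 5, so 1 − 60/365 = 0.836
- R = 14: Σk²/Σk = 1015/105 = 9.667, so 1 − 116/365 = 0.682

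For the year, k replaces 12k:

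- R = 7: 1 − 5/365 = 0.986
- R = 14: 1 − 9.667/365 = 0.974

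Enumerating every pair gives the same values:

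| Onset date recorded | Flagged, 7-day run-in | Flagged, 14-day run-in | Imputed start on or after first dose |
|---|---|---|---|
| Nothing | 100% | 100% | none (null) |
| Year only | 98.6% | 97.4% | 0% |
| Month and year | 83.6% | 68.2% | 0% |

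The last column is the contradiction: the flag puts these events after first dose, and the imputed date never does.

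The requirement that the AE had ended matters. Without it, onset is spread evenly over the run-in and the mean of k is (R + 1)/2 = 4 or 7.5. The same-month shares are then 1 − 48/365 = 87% and 1 − 90/365 = 75%. Those are too high here, because events that are already over began earlier on average.

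**After the fix.** With a complete end date before first dose, the share misflagged is 0% in every row. If the day is missing from both onset and end, 84% or 68% remain flagged, because the guard needs a complete end date and SAP 12.2.1.1 imputes a partial end date as late as possible.

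**The case against.** The strongest defence is that the SAP already gives the right answer for most of these events. With a partial onset and a complete pre-dose end date, the guard and cap always put the imputed start before first dose, and 6.3.2 states the correct definition. On that reading the opening rule is loose drafting. This stands in part: for partial onsets the fault is that no precedence is stated. It does not cover a fully missing onset, where no start is imputed and the flag goes uncorrected.

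A second defence is that calling unknown onsets treatment-emergent is conservative, since it over-counts events instead of hiding them. That suits real uncertainty. Here a recorded end date has removed the uncertainty that matters.

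Third, few events should be affected. Protocol 12.3 requires the onset date to be documented, AEs are asked about at every visit, and Visit 1 comes only 7 to 14 days after Screening. This stands.

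A reader might also infer that AEs in subjects who leave during the run-in are lost. The argument would be that "Except otherwise stated, the analysis set for all safety analyses is the Safety Analysis Set as defined in Section 3", and that this set requires exposure to post-randomisation product. The documents do not support so strong a reading:

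- SAP 6.3.2 puts AEs between consent and first masked exposure in a listing on the Screened Set.
- SAP 4.1 summarises the reasons for screening failure.
- The rationale for protocol Amendment 3 shows that leaving saline-only subjects out of the Safety Analysis Set was deliberate.
- The planned numbers bound the subjects concerned at 242 − 220 = 22 of 242 (9%). The true figure could be zero, because saline is dispensed only once the Screening criteria are met.

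What remains is that 6.3.2 does not name the set for the run-in presentation. That is missing detail, not an error.

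**Conclusion.** The point holds for AEs with a missing or partial onset date and a recorded end date before first dose. For these, the opening rule of 12.2.1.2 contradicts both the definition in 6.3.2 and the section's own guard and cap. Among such AEs lying wholly within the run-in and having a complete end date, it flags 100% (onset fully missing), about 97–99% (year only) or about 84% to 68% (day missing, 7- to 14-day run-in). These shares assume evenly spread first-dose dates and equally likely onset/end pairs.

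They are shares of a number that the documents do not give and that is probably small. It would be wrong to infer that run-in AEs in general are misallocated, because those with complete dates are classified correctly. Nor do the documents suggest that the flag favours either product: the events precede masked dosing, and the safety analysis is descriptive. This is a limited classification error in a stated rule, worth correcting because the correction is so cheap.

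**What to change.** Add to the opening rule of SAP 12.2.1.2: *unless the recorded AE end date is before the date of first study treatment (TRTSTD), in which case the AE is not treatment-emergent and is reported as a run-in AE; this condition overrides the rule above.*

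AEs whose end date is itself partial would stay flagged under the conservative rule, which is reasonable because their timing really is unknown.

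The cost is one sentence and one programming condition. No new data are needed, since AEs and their dates are collected from consent onwards. SAP 11.1 records that, at version 3.0, the database was not locked and the treatment code was unbroken, so the change could have been made masked at that point.

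Optionally, 6.3.2 could name the analysis set and denominator for the run-in AE presentation. That is a clarification only.

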12.2.2 Concomitant medication date imputation

12.2.2.1 Concomitant medication end date

To impute concomitant end date:

1. If the concomitant end date year value is missing, the date uncertainty is too high to impute a rational date. Therefore, if the concomitant end year value is missing or ongoing, the imputed concomitant end date is set to NULL.
2. Else, if the concomitant end date month is missing, the imputed end date should be set to the earliest of the (study treatment follow up period date, 31DECYYYY, date of death).
3. If the concomitant end date day is missing, the imputed end date should be set to the earliest of the (study treatment follow up period date, last day of the month, date of death).

If the imputed concomitant end date is less than the existing concomitant start date, use the concomitant start date as the imputed concomitant end date.

12.2.2.2 Concomitant medication start date

Concomitant treatments with partial start dates will have the date or dates imputed. Partial concomitant treatment start dates are imputed with reference to the first administration of study treatment (TRTSTD) in accordance with the rules outlined below.

	Day	Month	Year
Partial AE Start Date	Not used	MON	YYYY
Study Treatment Start Date (TRTSTD)	Not used	TRTM	TRTY

The following matrix explains the logic behind the imputation.

Comparison of month section	MON missing	MON<TRTM	MON=TRTM	MON>TRTM
YYYY missing	(C) Uncertain	(C) Uncertain	(C) Uncertain	(C) Uncertain
YYYY<TRTM	(D) = 01JULYYYY Before Study Treatment Start	(A) = 15MONYYYY Before Study Treatment Start	(A) = 15MONYYYY Before Study Treatment Start	(A) = 15MONYYYY Before Study Treatment Start
YYYY=TRTY	(C) Uncertain	(A) = 15MONYYYY Before Study Treatment Start	(C) Uncertain	(B) = 01MONYYYY After Study Treatment Start
YYYY>TRTY	(E) = 01JANYYYY After Study Treatment Start	(B) = 01MONYYYY After Study Treatment Start	(B) = 01MONYYYY After Study Treatment Start	(B) = 01MONYYYY After Study Treatment Start

The following table is the legend to the logic matrix.

Relationship	
Before Study Treatment start	Partial date indicates CMD start date prior to Study Treatment Start Date
After Study Treatment start	Partial date indicates CMD start date after Study Treatment Start Date
Uncertain	Partial date insufficient to determine relationship of CMD start date to Study Treatment Start Date
Imputation calculation	
NC / Blank Uncertain	No convention
(A) Before Study Treatment Start	15MONYYYY
(B) After Study Treatment Start	MAX(01MONYYYY, TRTSTD+1)
(C) Uncertain	IF CMDTYP1C IN (1, 3) THEN TRTSTD-1 ELSE IF CMDTYP1C IN (. 2) THEN TRTSTD+1
(D) Before Study Treatment Start	01JULYYYY
(E) After Study Treatment Start	01JANYYYY

To compute concomitant start date:

1. If the concomitant start date year value is missing, the imputed concomitant start date is set to one day prior to study treatment start date.
2. If the concomitant start date year value is less than the study treatment start date year value, the concomitant started before study treatment. Therefore:
 - a. If the concomitant month is missing, the imputed concomitant start date is set to the mid-year point (01JULYYYY).
 - b. Else if the concomitant month is not missing, the imputed concomitant start date is set to the mid-month point (15MONYYYY).
3. If the concomitant start date year value is greater than the study treatment start date year value, the concomitant started after study treatment. Therefore:
 - a. If the concomitant month is missing, the imputed concomitant start date is set to the year start point (01JANYYYY).
 - b. Else if the concomitant month is not missing, the imputed concomitant start date is set to the month start point (01MONYYYY).
4. If the concomitant start date year value is equal to the study treatment start date year value:
 - a. And the concomitant month is missing or the concomitant month is equal to the treatment start date month, then the imputed concomitant start date is set to one day prior to study treatment start date.
 - b. Else if the concomitant month is less than the treatment start date month, the imputed concomitant start date is set to the mid-month point (15MONYYYY).

- c. Else if the concomitant month is greater than the treatment start date month, the imputed concomitant start date is set to the month start point (01MONYYYY).

If complete (imputed) concomitant end date is available and the imputed concomitant start date is greater than the (imputed) concomitant end date, then imputed concomitant start date should be set to the (imputed) concomitant end date.

12.2.3 Other imputations

The age of subjects with a completely missing date of birth will be set to missing. If a subject's date of birth is partially missing then:

- If the year is missing then the age will be set to missing
- Else if the month is missing then the day will be set to 01 and the month will be set to July
- Else if the day is missing then the day will be set to 15.

If a subject has a partially missing date of birth and an imputed age of 17 years then this will be set at 18 years. However, if the imputed age were 16 years then the imputed age will remain at 16 years.

Missing baseline data of a primary/ key secondary variable may be imputed for use as a sensitivity analysis.

Other missing baseline data will not be imputed. This includes variables which are not allowed to be collected according to local regulations (e.g. race in France).

Date/Time (mm/dd/yyyy GMT):	Signed by:	Justification:
07/19/2018 12:55:29	[REDACTED]	[REDACTED]
07/19/2018 14:21:48	[REDACTED]	[REDACTED]
